The Effectiveness of TECH: Tablet Enhancement of Cognition and Health

NCT02955277

March 2020

OBJECTIVES

To establish the effectiveness of the ‘Tablet Enhancement of Cognition and Health’ (TECH), a novel cognitive intervention for improving global cognition, specific cognitive components, and health-related quality of life (HRQoL) in older adults with Mild Cognitive Impairment (MCI), compared with a control group.

METHODS

Study design

This is a single-blind randomized controlled trial (clinical trial number NCT02955277) with assessments administered pre and post the 5-week intervention, and at 6-month follow-up, by assessors blind to group allocation.

Population

Community dwelling older adults (>65 years) were recruited from two community geriatric clinics due to their memory problems, and were referred to the study by their family or geriatric physician. Inclusion criteria were as follows: a) a diagnosis of MCI, as determined by a score of 19-25 points on the Montreal Cognitive Assessment (MoCA), a valid and reliable tool, subjective memory complaints supported by a family member, and independence in basic and instrumental activities of daily living (BADL, IAD), b) normal or corrected vision and hearing, c) written and spoken fluency of the language, and d) ability to use a touchscreen tablet after an initial demonstration. Individuals were excluded if they experienced severe depressive symptoms (Geriatric Depression Scale > 10 points), and if they were diagnosed with dementia, or other neurological or psychiatric conditions. All participants signed informed consent forms before participating in the study.

Tools

Outcome measures

The **Primary outcome measure** was MoCA (Nasreddine et al., 2005), for assessing global cognition, which was also used to screen for eligibility. **Additional cognitive assessment** included the WebNeuro assessment (Silverstein et al., 2007) which is A valid computerized assessment battery including the assessments of the following specific cognitive components/domain (subtests): Sustained attention (Continuous Performance Task), 22 controlled attention (Verbal Interference Task), flexibility (Switching of Attention Task), inhibition (Go-NoGo Task), working memory (Digit Span Task), memory recall (Memory Recall Task), problem solving (Maze Task). For each domain a raw score was calculated, and then converted to a z score, with a normative average of 0, and a standard deviation of 1. Higher scores for each domain indicates better performance. The secondary outcome measures included The Tower of Hanoi (ToH) task (Simon, 1975), a commonly used goal-directed measure assessing problem-solving, and specifically, planning. A computerized version of the task was used (<http://vornlocher.de/tower>). The participants completed the first three (out of six) levels of the task. the number of moves per level, and time for completion were recorded. the 12-Item Short Form Health Survey (SF-12) (Ware, Snow, Koskinski, & Gandek, 1993) for measuring health-related quality of life; physical and mental composite summary scores (Wilson, Tucker, & Chittleborough, 2002), higher scores indicating better health measures (Ware et al., 1993). The General Self-Efficacy Scale (GSES) (Schwarzer& Jerusalem, 1995), which is highly reliable and valid scale for assessing optimistic self-beliefs to cope with a variety of difficult demands in life. It consists 10 statements such as

'I can solve most problems if I invest the necessary effort'. The total score ranges from 10 to 40. Higher scores represent higher levels of general self efficacy (Schwarzer & Jerusalem, 1995). In addition, demographic information and previous experience with technology use (computer, smartphone and tablet) were collected.

The Intervention

The TECH intervention (study group) included daily self-training facilitated by weekly group sessions. Participants received iPads to take home and were requested to play puzzle-game apps, which simultaneously provided practicing different cognitive components, 3-5 times a week X 30-60 minutes, for a total of 15-25 training sessions. Weekly one-hour sessions led by an occupational therapist (OT) took place in a small group setting (4-6 participants) over a five-week period. These sessions focused on teaching tablet operation, allowing participants to explore and practice new apps, and increasing their confidence and independence in using and activating the tablet.

Standard care (control group). Participants received standard occupational therapy care for MCI including either a) a single consultation in a group setting (4-6 participants) to encourage participants to engage in activities such as solving crossword puzzles or playing board or card games in their leisure time to stimulate cognitive function; or b) participation in a social group (six one-hour sessions of 4-6 participants) of playing puzzle board games, with no recommendation to perform self-training at home.

Procedure

Participants were approached by phone and were provided with information about the study. Those who were willing to participate were invited to the geriatric clinic for the assessment session. After signing an informed consent form, the MoCA, GDS, BADL,

and IADL questionnaires were administered to confirm eligibility. If the participants were found eligible, the remaining outcome measures were administered. Then participants were stratified according to low (19-22 points) or high (23-25 points) MoCA score and then randomly allocated to the TECH or control group using a 1:1 ratio. Allocation was concealed from the investigators and the enrolled participants. Participants were notified by phone about their allocation. The assessors, who were blind to group allocation, were OTs trained to assess the study. Participants who were invited to the post- and follow-up assessment sessions were asked not to discuss the intervention with the assessors.

Data analysis

'IBM SPSS Statistics 25' software was used for descriptive statistics to characterize the sample and outcome measures for the three assessments. Since the outcome measures were not normally distributed, non-parametric tests were performed. Intention-to-treat analysis was conducted with the last observation carried forward method, which is an acceptable data imputation method.²⁶ The percentage change was calculated for MoCA, WebNeuro, and SF-12 measurements between pre and post and between pre and follow-up using these formulas[(post-pre)/pre*100%], [(follow-up-pre)/pre*100%]. The difference between groups for the percentage change was tested using the Mann Whitney Test. Since significance tests are highly dependent on the sample size, the effect size was also estimated by using the effect size formula for non-parametric tests: Cohen's $r=Z/\sqrt{N}$. The Z value was retrieved from the Mann Whitney test U output. Cohen's r effect size values were considered small (0.1), medium (0.3), and large (0.5).

In each group, we calculated the percentage of participants who achieved the Minimal Clinically Important Difference (MCID) improvement in global cognition. MCID is defined as the smallest change in scores perceived by the patient as beneficial, which could lead to a change in the patient's treatment. In this study, the MCID of the MoCA was considered an improvement of at least 1.22 points, as found in Stroke Rehabilitation (since MCID data for individuals with MCI, to the best of our knowledge, have not yet been established).

The sample size was calculated using 'G*Power 3.1.9.4' software, according to a small effect size, based on previous studies assessing the effectiveness of computerized cognitive training for older adults with MCI, with 80% power and a significance level of 0.05. A sample size of 68 participants was calculated. Taking into consideration a 20% drop-out rate, 80 participants were required.

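### WebNeuro's seven domains serve a stated effectiveness objective but sit outside the outcome hierarchy, and up to 14 unadjusted between-arm tests substantially inflate the error rate for any specific-component claim

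*Combined protocol and SAP*

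**What the plan says.** The Objectives section of the combined protocol and SAP sets out to establish effectiveness for "improving global cognition, specific cognitive components, and health-related quality of life (HRQoL"), so specific components are a target in their own right beside global cognition and quality of life.

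The Outcome measures section then ranks the instruments:

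- Primary: "The Primary outcome measure was MoCA".
- Between primary and secondary: "Additional cognitive assessment included the WebNeuro assessment".
- Secondary: "The secondary outcome measures included The Tower of Hanoi (ToH) task", followed by SF-12 and the self-efficacy scale.

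The WebNeuro battery is introduced as "including the assessments of the following specific cognitive components/domain (subtests"), and seven domains follow, from sustained attention to problem solving. On scoring, the text says "For each domain a raw score was calculated, and then converted to a z score". The normative mean is 0, the standard deviation is 1, and higher is better. No total or composite is defined.

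The Data analysis section takes percentage change for MoCA, WebNeuro and SF-12 "between pre and post and between pre and follow-up", and adds: "The difference between groups for the percentage change was tested using the Mann Whitney Test". It names no key domain or visit for WebNeuro, and gives no testing order, multiplicity rule or statement that these results are exploratory. The 0.05 level appears once, in the sample-size paragraph.

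**The concern.** The instrument that most directly serves one of the three stated objectives has no place in the outcome hierarchy. The natural reading of the analysis text is one Mann-Whitney comparison per domain per visit. No rule says what pattern of results would count as an effect on specific components, so nothing in the plan prevents one or two significant domains from being presented as a selective cognitive benefit.

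What is at stake is the credibility of that claim. A reader who sees a domain with p < 0.05 would assume the usual protection against chance, and the plan does not provide it.

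**Working it through.** The document states no family-wise error rate, so there is no figure of its own to reproduce. The check is to count the tests and compute the chance of a false positive when TECH has no effect.

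**Inputs**

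- Domains: 7 (Outcome measures).
- Comparisons in time: 2, pre to post and pre to follow-up (Data analysis).
- Tests: 7 × 2 = 14. Separate testing of each domain is inferred from seven scores with no composite.
- Level: 0.05 per test, inferred as the only level given. Two-sided tests are assumed; sidedness is not stated.
- Correlations between domains and between visits: not given, so a range is assumed.

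**Independent tests**

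Any significant result, either direction:

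- one visit: 1 − 0.95^7 = 30.2%
- both visits: 1 − 0.95^14 = 51.2%

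At least one significant result favouring TECH (0.025 per test):

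- one visit: 1 − 0.975^7 = 16.2%
- both visits: 1 − 0.975^14 = 29.8%

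**Correlated tests**

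Null Z statistics were simulated from a multivariate normal distribution (300,000 draws, critical value 1.96). The correlation between two statistics is the product of the domain and visit correlations.

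| Domain correlation | Visit correlation | 14 tests, either direction | 14 tests, favouring TECH |
|---|---|---|---|
| 0 | 0 | 51% | 30% |
| 0.3 | 0.5 | 44% | 23% |
| 0.5 | 0.7 | 36% | 18% |
| 0.7 | 0.8 | 26% | 13% |
| 0.7 | 0.9 | 24% | 12% |

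With one visit only (7 tests), domain correlations of 0.3, 0.5 and 0.7 give 27%, 23% and 18% in either direction, and 14%, 12% and 9% favouring TECH.

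Zero correlation between visits is a bounding case. Both changes share the same baseline, and last observation carried forward copies post values into follow-up for later dropouts. Both features raise the visit correlation and lower the inflation, which is why the table extends to 0.9.

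Against the nominal rates, the inflation in either direction is 24/5 to 51/5, about 5- to 10-fold. Favouring TECH it is 12/2.5 to 30/2.5, about 5- to 12-fold.

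**With adjustment**

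- Seven tests at 0.05/7 = 0.0071: 1 − (1 − 0.05/7)^7 = 4.9% if independent.
- Fourteen tests at 0.05/14 = 0.0036: 1 − (1 − 0.05/14)^14 = 4.9% if independent.

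**The change metric**

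The plan's formula is (post − pre)/pre × 100%. Take a participant one standard deviation below the norm who improves to the norm: pre = −1, post = 0. The result is (0 − (−1))/(−1) × 100% = −100%, so an improvement is scored as a decline. At pre = 0 the formula is undefined. Adjusting p-values computed on this metric would not make the direction of a WebNeuro result reliable.

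**The case against.** The best defence is that MoCA is the single named primary outcome and WebNeuro is only additional, so formal family-wise control is not obligatory. It stands in part: the WebNeuro tests do not touch the primary MoCA claim, and an explicit exploratory label would be an adequate answer. But the plan gives no such label, and its objective is to establish effectiveness on these components.

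A second defence is that an effect size accompanies each test. It gives no protection, because r = Z/√N uses the same Z. With N = 80, a chance result at Z = 1.96 gives r = 1.96/√80 = 0.22, already above the plan's threshold of 0.1 for a small effect.

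A reader might infer that a false claim of benefit is likely, meaning more probable than not. The documents do not support that. Only the either-direction figure under full independence passes one half (51%), and it counts results favouring control. Results favouring TECH reach at most about 30%, and independence is implausible for seven tests on the same people.

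A reader might also infer that the plan prescribes 14 tests at 0.05. It does not say so. Separate domain tests and that level are strong inferences, since no composite and no other level are given.

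**Conclusion.** The point holds as one of substantially inflated error. If TECH has no effect, at least one of up to 14 WebNeuro comparisons would be nominally significant with probability of about 24–51% in either direction, and about 12–30% in TECH's favour against a nominal 2.5%.

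The range assumes two-sided 0.05 tests, all null hypotheses true, domain correlations of 0–0.7 and visit correlations of 0–0.9. The inflation is clear throughout it. It bears only on claims about specific cognitive components.

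**What to change.** In Data analysis, and in any report:

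1. Treat WebNeuro domain results as exploratory by default and report all 14 comparisons.
2. Claim an effect on a specific component only if it survives Holm. The family is either all 14 comparisons (smallest p against 0.0036), or the seven domains at the post-intervention visit (smallest p against 0.0071) with follow-up as supportive. The 14-test family needs no choice of visit, which makes it the safer one if results have been seen.
3. Run these tests, and any seven-domain composite, on change in z units (post minus pre, or follow-up minus pre), not on percentage change.
4. State that the composite, visit and adjustment are post hoc if they were chosen after data were seen. The section is written in the past tense and reports that outcomes were not normally distributed, so data had already been examined. Adjustment now would discipline the claim but would not restore prespecification.

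The cost is a few lines of text and a re-run, with no new data or participants, and less power for any single domain. As a normal-approximation illustration, 68 evaluable participants give 80% power at 0.05 for a standardised difference of 0.68. Power for that difference falls to 54% at 0.05/7 and 46% at 0.05/14; Holm does no worse than these.

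A composite can recover power when effects are spread across domains. With 40 per arm, 0.3 SD in every domain and an assumed domain correlation of 0.3, the composite has 56% power, against 9% for one domain at 0.05/7. A composite result alone would not support a claim about a specific component.

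### Baseline technology experience is collected but not used in the WebNeuro comparisons, which gives up a small amount of precision at no saving; the unadjusted test remains valid.

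*Combined protocol and SAP*

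**What the plan says.** The Outcome measures section describes WebNeuro as a computerised battery covering seven cognitive domains, each reported as a z score with a normative mean of 0 and SD of 1. It closes by recording that "demographic information and previous experience with technology use (computer, smartphone and tablet) were collected". No scale, coding or expected distribution is given for that experience.

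Under Procedure, people were first "stratified according to low (19-22 points) or high (23-25 points) MoCA score". After that step, each person was "randomly allocated to the TECH or control group using a 1:1 ratio". Technology experience is not a stratification factor.

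Under Data analysis, "The percentage change was calculated for MoCA, WebNeuro, and SF-12 measurements between pre and post and between pre and follow-up", and "The difference between groups for the percentage change was tested using the Mann Whitney Test". No covariate, stratum, subgroup or sensitivity analysis is named. Descriptive statistics are planned to characterise the sample, so technology experience may appear in a baseline table, but it has no stated role in comparing the arms.

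**The concern.** WebNeuro is the measure that addresses the objective on specific cognitive components, and it is taken on a computer. Someone new to devices may gain differently on repeat testing from someone already at ease with them. The eligibility rule asks only for the ability to use a tablet after a demonstration, so novices can enrol. With 80 participants and no balancing on experience, the arms can differ noticeably on it by chance.

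If experience does predict WebNeuro change, the unadjusted comparison carries variation that could have been removed with data already held. A reader who then sees an uneven baseline table has no planned analysis to turn to, and a decision to adjust made at that stage would depend on the data.

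The point concerns experience before randomisation. The tablet teaching given to the TECH arm comes after randomisation, and baseline adjustment cannot remove its effect.

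**Working it through.** The plan gives no figure for the influence of technology experience, so there is nothing of its own to reproduce.

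**Inputs from the documents:** 80 participants required and 1:1 allocation, hence 40 per arm; intention-to-treat analysis with last observation carried forward, so all 80 are taken as analysed; a small effect is r = 0.1, about d = 0.2 at 1:1.

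**Assumptions (the documents are silent):** 30-70% of participants are experienced; experienced and inexperienced users differ by 0.3-0.5 SD in WebNeuro change; experience is unrelated to MoCA band.

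**1. Chance of imbalance.** With K experienced among 80 and X of them in one arm of 40, X is hypergeometric and the arms differ by |2X − K| people. Six people are 15 percentage points and eight are 20.

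| K experienced | P(gap ≥ 15 points) | P(gap ≥ 20 points) |
|---|---|---|
| 40 (50%) | 0.263 | 0.117 |
| 24 or 56 (30% or 70%) | 0.222 | 0.087 |

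**2. Shift in the arm difference at a 20-point gap.** Shift = gap × difference between user groups:
- 0.20 × 0.3 = 0.06 SD
- 0.20 × 0.5 = 0.10 SD

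Against d = 0.2 this is 30-50%. Against the effect that 40 per arm can detect with 80% power, two-sided (d = 0.63), it is 0.06/0.63 = 0.10 to 0.10/0.63 = 0.16. On the r scale (about d/2) the shift is 0.03-0.05. The 95% sampling range of r under no effect is ±1.96/√80 = ±0.22.

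**3. Precision gained by adjustment.** The same assumption fixes the correlation: rho = difference × √(p(1 − p)).
- Low end: 0.3 × √(0.3 × 0.7) = 0.14; rho² = 0.019
- High end: 0.5 × √(0.5 × 0.5) = 0.25; rho² = 0.0625

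Adjustment therefore removes about 2-6% of variance. Equivalent extra participants: 80/(1 − 0.019) − 80 = 1.5 to 80/(1 − 0.0625) − 80 = 5.3. Reduction in standard error: 1 − √(1 − rho²) = 1% to 3%. Estimating one more coefficient costs roughly 1/(80 − 4) = 1.3% of variance, so the low end is almost cancelled.

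**4. Sensitivity to the assumed correlation.** The 95% limit of chance imbalance is 1.96 × √(4/80) = 0.44 covariate SDs, or 22 points for a factor split 50:50. The shift in d is rho × 0.44:

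| rho | Shift in d | Share of d = 0.2 |
|---|---|---|
| 0.1 | 0.044 | 22% |
| 0.2 | 0.088 | 44% |
| 0.3 | 0.131 | 66% |
| 0.5 | 0.219 | 110% |

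**5. Validity of the unadjusted test.** In 10,000 simulated trials per setting, at N = 68 and N = 80 with rho of 0, 0.3 and 0.5, the Mann-Whitney Type I error at nominal 0.05 lay between 0.047 and 0.052.

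**The case against.** The strongest reply is that nothing here is an error. An unadjusted comparison after randomisation is valid, stratifying on the primary outcome's baseline band is a legitimate choice, and recording a variable without adjusting for it contradicts nothing. That stands, and step 5 supports it.

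A reader might infer that the WebNeuro results are biased, or that imbalance can move them by at most half a small effect. The documents support neither. Chance imbalance is already inside the test's sampling error. Half a small effect is the product of an assumed 0.5 SD difference and a 20-point gap that arises in about one trial in ten; step 4 shows the share running from about a fifth to more than the whole as the assumed correlation changes.

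The mechanism is also unproven. Only an association with change matters, not with level, and the requirement to manage a tablet after a demonstration may narrow the range of experience. Both could make the correlation smaller, but neither can be quantified from the documents.

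A further objection concerns the metric. Percentage change is unstable for z scores centred near 0, and where the pre score is negative an improvement yields a negative percentage. A shift in SDs of change does not carry over directly to that statistic, and stratifying the existing test by experience would leave the problem in place. This is correct and determines the form of the fix.

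Finally, the Data analysis section is in the past tense, so prespecification may no longer be possible.

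**Conclusion.** The point holds as a minor missed opportunity for precision, confined to the WebNeuro comparisons. MoCA is not described as computerised, and although the Tower of Hanoi task is, the plan describes no percentage-change comparison for it.

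The likely benefit is a standard error 1-3% smaller, before the cost of the extra coefficient, together with a settled answer if the arms prove uneven on experience. These sizes rest wholly on the assumed 0.3-0.5 SD difference and 30-70% prevalence. They are worked for change scores; in a model of the post score the relevant quantity is the association of experience with the post score given the pre score, which the documents do not give either. Confidence in the size is low; the textual facts are clear.

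**What to change.** Define one baseline technology-use variable, for example tablet or smartphone user yes/no, without reference to arm or outcome. For each WebNeuro domain, model the post score with arm, pre score and this variable as terms, on ranks if the scores are not normally distributed. Do the same for the follow-up score. Do not instead stratify a test of percentage change in z scores. Keep the unadjusted comparison as a sensitivity analysis, and show technology experience by arm in the baseline table. If outcomes by arm have already been examined, label the adjusted analysis post hoc.

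The cost is a paragraph of analysis-plan text, minor programming and one degree of freedom per model. No new data are needed. If experience does not predict change, there is little or nothing to gain.

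### Last observation carried forward is the only missing-data method, so the 6-month comparison partly assumes that the post result lasted, and nothing tests that assumption

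*Combined protocol and SAP*

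**What the plan says.** Study design sets out three time points: "assessments administered pre and post the 5-week intervention, and at 6-month follow-up". Data analysis then computes percentage change for MoCA, WebNeuro and SF-12 "between pre and post and between pre and follow-up using these formulas", and compares the arms on it: "The difference between groups for the percentage change was tested using the Mann Whitney Test".

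On missing data there is a single sentence: "Intention-to-treat analysis was conducted with the last observation carried forward method, which is an acceptable data imputation method". A numbered reference supports it, and its source is not available here. No other missing-data method, no sensitivity analysis and no account of missingness by arm or visit is described. Missing data were expected, because the sample-size paragraph raises 68 participants to 80: "Taking into consideration a 20% drop-out rate".

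**The concern.** The follow-up comparison is the only one in the plan that bears on whether a benefit lasts. For someone assessed at post but not at 6 months, LOCF copies the post score into the follow-up slot, so that person's 6-month change equals the post change by construction. The text gives no reason of its own why MoCA should stay flat between those visits in people with MCI.

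The rule acts differently on people lost before post. On the natural reading, which the text does not spell out, their pre score is carried to both later visits and they enter with 0% change. That can also distort the pre-to-post comparison, but only if they would have gained.

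At stake is interpretation. With LOCF alone, a reader cannot tell how much of a 6-month difference, or of its absence, comes from carried-forward scores.

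**Working it through.** **The plan's own figures.** The 20% allowance does not give 80: 68/(1−0.20) = 85 and 68 × 1.20 = 81.6. The 12 participants between 68 and 80 are 12/80 = 15%. Both 15% and 20% are therefore used below.

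**Inputs.** From the documents: 20% drop-out, entry MoCA 19–25, 80 participants allocated 1:1 (40 per arm), and an effect of 1.22 points, the plan's minimal important difference ("the MCID of the MoCA was considered an improvement of at least 1.22 points"). Assumed: change SD 2, correlation 0.5 between post and 6-month change, loss unrelated to scores within arm, and the fading, decline and arm-specific losses shown.

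**Formula, equal loss.** Let a be the share lost after post, b the share lost before post, P the post effect and F the 6-month effect in completers.

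- LOCF 6-month contrast = a × P + (1−a−b) × F. With b = 0 this is (1−w) × F + w × P, where w = a.
- Standard error of a difference in means = 2 × √(2/40) = 0.447.

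**Effect fades fully (F = 0), P = 1.22 unless stated.** With unequal loss and a 1-point decline in both arms, each arm's mean is worked separately and subtracted. The last column is the share of 4000 simulated trials per setting in which the Mann-Whitney test on LOCF percentage change rejected at 5%. Ranges span repeat runs.

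| Loss, TECH/control | Decline | Arithmetic | Spurious difference | Rejection |
|---|---|---|---|---|
| 20/20 after post | none | 0.20 × 1.22 | +0.244 | 7.1–7.6% |
| 15/15 after post | none | 0.15 × 1.22 | +0.183 | about 6.6% |
| 10/10 after, 10/10 before | none | 0.10 × 1.22 | +0.122 | 5.4% |
| 20/20 before post | none | 0 × 1.22 | 0 | 5.8% |
| 20/20 after post, P = 0.4 | none | 0.20 × 0.4 | +0.08 | 4.8% |
| 30/10 after post | none | 0.30 × 1.22 | +0.366 | about 11–12% |
| 30/10 after post | 1 point | 0.366 − 0.70 + 0.90 | +0.566 | about 17% |
| 10/30 after post | 1 point | 0.122 − 0.90 + 0.70 | −0.078 | 5.2% |
| 15/25 after post | 1 point | 0.183 − 0.85 + 0.75 | +0.083 | 4.3% |

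Simulation error is about ±0.7 percentage points at 5% and about ±1 at 12% (1.96 × √(0.12 × 0.88/4000) = 1.0).

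On the plan's scale, 0.244/22 is about 1.1 percentage points of change, taking 22 as the middle of the entry range. In standard errors, 0.244/0.447 = 0.55 and 0.183/0.447 = 0.41. In the first row, within-arm multiple imputation gave 0.00 points and 4.3% rejection; a complete-case Mann-Whitney gave 0.00 and 4.7–5.0%.

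**Loss before post, lasting effect (P = F = 1.22, b = 0.20).** LOCF gives 0.80 × 1.22 = 0.976 and within-arm imputation gives 1.22. The truth is 1.22 × (0.80 + 0.20 × g), where g is the fraction of the effect that early leavers would have gained.

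| g | Truth | LOCF error | Imputation error |
|---|---|---|---|
| 1 | 1.22 | −0.244 | 0 |
| 0.5 | 1.098 | −0.122 | +0.122 |
| 0 | 0.976 | 0 | +0.244 |

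Rejection in this setting is 60.3% with LOCF and 61.7% with imputation, against 72.3% with no loss. Changing the method moves the estimate but does not recover power.

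**The case against.** The case for leaving the plan alone has real strength.

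- **The first row is close to the worst case for equal loss.** It needs full fading, all loss after post and 20% lost. The other equal-loss settings give +0.18 points or less, and apart from the 15/15 case their rejection is near nominal. This stands and limits the size of the point.
- **Imputation is not shown to be better than LOCF.** If early leavers would have gained nothing, LOCF is right and within-arm imputation overstates the effect by 0.24, as large as LOCF's error in the first row. This stands. A reader might infer that imputation should replace LOCF as the main analysis; the documents do not say which kind of loss dominates, so they do not support that.
- **A complete-case test did as well.** Where loss is unrelated to scores within arm, any method that drops carried-forward values does well. This stands, and the simpler option is offered below.
- **The document is dated March 2020 and written in the past tense.** A new main analysis now would be post hoc. This stands.
- **The objectives do not mention durability.** This stands only in part. No visit is named as primary, and the plan does test change to 6 months, so that comparison cannot be set aside as minor.
- **The supporting reference cannot be seen.** Whether its rationale is adequate cannot be judged. The arithmetic above does not depend on it.

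**Conclusion.** The point holds as a modest, inexpensive improvement. With LOCF as the only method, the 6-month contrast is pulled towards the post effect by the share lost after post, and the plan contains nothing that would reveal it. With equal loss and full fading the distortion is about +0.24 points at 20% loss (7–8% rejection) or +0.18 at 15% (about 6.6%). It is larger only in the cases where TECH loses many more participants than control (30/10): about 11–12% rejection without decline and about 17% with a 1-point decline in both arms. These figures rest on the assumed SD, correlation, fading and loss patterns.

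Two stronger readings are tempting and unsupported:

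- **That LOCF favours TECH in this trial, or that its 6-month result is wrong.** Loss by arm and visit is not given, and the direction can reverse, as the 10/30 row shows.
- **That the pre-to-post comparison is compromised.** Loss after post does not touch it. Loss before post biases it only if early leavers would have gained.

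**What to change.** 1. Report missingness by arm and visit, with reasons where known. This would show at once whether the concern is large.
2. Keep LOCF and add a missing-at-random analysis beside it for the post and 6-month comparisons of MoCA, WebNeuro and SF-12. Prespecify it, or label it clearly as post hoc if the data have already been analysed. One form is multiple imputation within arm, using pre, post and the MoCA stratum used at randomisation ("stratified according to low (19-22 points) or high (23-25 points) MoCA score"), with the Mann-Whitney probability U/(n1 × n2) pooled by Rubin's rules. The simpler form is a complete-case Mann-Whitney test.
3. For MoCA, shift imputed TECH scores by 0, −1 and −2 points at both visits and report the shift at which the conclusion changes. At 20% TECH loss, shifts of −1 and −2 move the difference by −0.20 and −0.40. A shift of −1.22 for early leavers would represent no gain, which lies inside this range. Add a case in which TECH participants lost before post are imputed from the control arm. This step needs imputed scores even if the complete-case form is chosen in step 2.
4. Claim benefit at 6 months only if LOCF and these analyses agree.

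The cost is some extra analysis of scores already collected, with no new visits or participants. The downside is a missing-at-random assumption that cannot be verified and that overstates the effect if early leavers would have gained nothing. Step 3 is there to expose that.
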